7.9.3 Subject Disposition

The number of subjects included in each analysis population (randomized, ITT, safety and PP) will be summarized by treatment group, by treatment group within analysis center and by treatment group within investigational site. The number of subjects completed and discontinued (including the primary reason for discontinuation) will be summarized for each treatment group.

Subjects who are excluded from an analysis population will be summarized by the reasons for exclusion. Reasons subjects were not randomized will be summarized for subjects who did not enroll in the study.

7.9.4 Protocol Deviations

Protocol deviations will not be entered into the database. Only deviations leading to exclusion from analysis populations will be identified and summarized.

7.9.5 Demographic and Baseline Characteristics

All baseline summaries will be performed on the ITT, PP and safety populations.

Sex, race, ethnicity and Fitzpatrick skin type will be summarized by counts and percentages. Age will be summarized with descriptive statistics. Summaries of dichotomized age (less than median and greater than or equal to median) and categorized age (less than 18, 18 to less than median and greater than or equal to median) will also be included.

Subjects' baseline characteristics related to efficacy analyses will be summarized and compared between treatment groups to evaluate baseline balance between the treatment arms. Baseline inflammatory lesion count and baseline non-inflammatory lesion count will be compared using a two-way analysis of variance with factors of treatment group and analysis center. Baseline IGA will be compared using a Cochran-Mantel-Haenszel test of row means scores, stratified by analysis center.

Acne vulgaris history, including number of years since onset, anatomical areas affected and prior acne treatments, will be summarized by counts and percentages. If only the year is known for start of acne vulgaris the number of years since onset will be calculated by using January for month and "01" as day. If only the year and month are known for start of acne vulgaris then onset will be calculated by using "01" as day.

Medical histories will be coded using the MedDRA dictionary and presented in a by-subject listing.

7.9.6 Prior and Concomitant Medications

Prior and concomitant medications will be coded to preferred name and anatomical therapeutic chemical (ATC) classification of ingredients using the WHO-DDE.

Counts and percentages will be provided to summarize the use of prior and concomitant medications other than the study drug reported throughout the study. The number and percent of subjects reporting medications will be summarized by ATC level 2 term and preferred name. Medications which start prior to first dose will be considered prior medications. Ongoing medications and medications ending after the date of first dose will be considered concomitant medications. Medications which are both prior and concomitant will be included in both summaries. Incomplete start and end dates which could be prior to first dose or after first dose will be considered prior to first dose.

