5.3.2 Exclusion Criteria

Subjects meeting any of the following criteria are not eligible for study participation:

1. Previous active treatment in Olumacostat Glasaretil (DRM01B) Gel trials

- 2. Females who are currently pregnant, lactating or planning to become pregnant during the course of the study
- 3. Known hypersensitivity to Olumacostat Glasaretil or its excipients
- 4. Any skin condition which may interfere with the evaluation of safety or, of acne vulgaris (e.g., rosacea; seborrheic dermatitis; perioral dermatitis; corticosteroid-induced acne or folliculitis)
- 5. Excessive facial hair that would interfere with diagnosis or assessment of acne vulgaris
- 6. Excessive sun exposure that could affect the clinical state of acne, in the opinion of the investigator or, anticipated use of tanning booths
- 7. Active cystic acne or acne congoblata, acne fulminans, and secondary acne
- 8. Two or more active nodulocystic lesions on the face
- 9. Screening clinical chemistry, hematology, or urinalysis laboratory value, deemed clinically significant, by the Investigator
- 10. Abnormal findings on screening ECG, deemed clinically significant by the Investigator
- 11. Subjects who are actively participating in an experimental therapy study or who have received experimental therapy within 30 days or 5 half-lives (whichever is longer) of the Baseline visit
- 12. Subjects who are a poor medical risk because of other systemic diseases or active uncontrolled infections, in the opinion of the investigator
- 13. Any other condition which, in the judgment of the investigator, would put the subject at unacceptable risk for participation in the study
- 14. Treatment with over-the-counter topical medications for the treatment of acne vulgaris including benzoyl peroxide, topical anti-inflammatory medications, corticosteroids, α-hydroxy/glycolic acid on the face within 2 weeks prior to Baseline
- 15. Treatment with systemic corticosteroids (use of intranasal and inhaled corticosteroids allowed for seasonal allergies and asthma) within 4 weeks prior to Baseline
- 16. Treatment with systemic antibiotics or systemic anti-acne drugs within 4 weeks prior to Baseline
- 17. Prescription topical retinoid use on the face within 4 weeks prior to Baseline (e.g., tretinoin, tazarotene, adapalene)

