11.2 Populations Analyzed

Listings and summaries will be provided for all randomized subjects.

Approximately 700 subjects with acne vulgaris on the face will be randomized, in a 2: 1 fashion, to Olumacostat Glasaretil Gel, 5.0% BID, or Olumacostat Glasaretil Gel, Vehicle. Efficacy analyses will be performed using the intent-to-treat (ITT) population and the per-protocol (PP) population. Safety analyses will be performed using the safety population.

All subjects who are randomized and dispensed study drug will be included in the ITT population.

All subjects who are randomized, receive at least one confirmed dose of study drug and have at least one post-baseline safety assessment will be included in the safety population.

The PP population will include all subjects in the safety population who complete the Week 12 evaluation without any significant protocol violations (i.e., any subject or investigator activity that could have possibly interfered with the therapeutic administration of the treatment or the precise evaluation of treatment efficacy). The PP population will include subjects in the safety population who do not meet any of the following criteria:

- Violated the inclusion/exclusion criteria;
- Have taken any interfering concomitant medications;
- Did not attend the Week 12 visit;
- Have missed both the Week 4 and Week 8 study visits;
- Have not been compliant with the dosing regimen (i.e. subjects must apply 80–120% of the expected applications of study medication during participation in the study);
- Out of visit window at the Week 12 visit by ± 5 days;

Subjects that discontinue from the study due to an adverse event related to study treatment or documented lack of treatment effect will be included in the PP population. Prior to breaking the blind, other additional criteria may be added to the list to accommodate for unforeseen events that occurred during the conduct of the trial that result in noteworthy study protocol violations.

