7.8.4 Per-Protocol (PP) Population

All subjects in the safety population who complete the Week 12 evaluation without any significant protocol violations will be included in the PP population and analyzed according to the treatment group they received. The PP population will include subjects in the safety population who do not meet any of the following criteria:

- Violated the inclusion/exclusion criteria;
- Have taken any interfering concomitant medication;
- Did not attend the Week 12 visit;
- Have missed both the Week 4 and Week 8 study visits;
- Have not been compliant with the dosing regimen (i.e. subjects must apply 80-120% of the expected applications of study medication during participation in the study);
- Out of visit window at the Week 12 visit by ± 5 days.

Subjects that discontinue treatment or from the study due to an AE related to study treatment or documented lack of treatment effect will be included in the PP population. Prior to breaking the blind, other additional criteria may be added to the list to accommodate for unforeseen events that occurred during the conduct of the trial that result in noteworthy study protocol violations.

All efficacy analyses will be performed on the PP population.

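### SAP 7.9.6 resolves every ambiguous medication end date to before first dose, so some on-study use can be classed as prior only

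*SAP*

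**What the plan says.** SAP section 7.9.6 gives two definitions and one rule for partial dates.

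- Prior: "Medications which start prior to first dose will be considered prior medications".
- Concomitant: "Ongoing medications and medications ending after the date of first dose will be considered concomitant medications".
- Partial dates: "Incomplete start and end dates which could be prior to first dose or after first dose will be considered prior to first dose".

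The same section lets a medication be both prior and concomitant, in which case it is counted in both summaries.

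The word concomitant appears again in the PP definition. SAP section 7.8.4 removes a subject on the criterion "Have taken any interfering concomitant medication", and Protocol section 11.2 has the same criterion ("Have taken any interfering concomitant medications"). Neither place gives a date rule for it or refers to SAP 7.9.6. On deviations generally, SAP section 7.9.4 says: "Protocol deviations will not be entered into the database"; only those that lead to exclusion from an analysis population are identified and summarised.

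**The concern.** The partial-date rule treats start and end dates alike, but the two do different work. A start date decides whether a medication is prior, and an end date decides whether it is concomitant. Moving a doubtful start date back costs nothing, because a medication that continues past first dose is still counted as concomitant. Moving a doubtful end date back removes the medication from the concomitant class. Every doubt about the end date is thus settled against on-study use.

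Two outputs could be affected. The first is the concomitant-medication summary. It matters because Protocol section 7.2 prohibits other acne treatments during the study and allows systemic antibiotics only for acute infection. The second is PP membership, and through it the efficacy analyses that SAP 7.8.4 and 7.9.7 repeat on that population.

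**Working it through.** The plan attaches no figure to this rule, so there is none to reproduce. The check is to apply SAP 7.9.6 to each combination of start and end date, then apply the opposite convention for ambiguous end dates and compare. Ambiguous means that the recorded part could fall on either side of first dose.

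| Start | End | SAP 7.9.6 | Ambiguous end counted as after |
|---|---|---|---|
| before | before | prior | prior |
| before | after | prior + concomitant | prior + concomitant |
| before | **ambiguous** | **prior only** | **prior + concomitant** |
| before | ongoing | prior + concomitant | prior + concomitant |
| ambiguous | before | prior | prior |
| ambiguous | after | prior + concomitant | prior + concomitant |
| ambiguous | **ambiguous** | **prior only** | **prior + concomitant** |
| ambiguous | ongoing | prior + concomitant | prior + concomitant |
| after | after | concomitant | concomitant |
| after | ambiguous | concomitant | concomitant |
| after | ongoing | concomitant | concomitant |

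Start after with end before is impossible. With start after and end ambiguous, the end cannot precede first dose, so the rule, read sensibly, does not apply. Two of the eleven possible rows differ, and both have an ambiguous end date. The rows with an ambiguous start and a later or ongoing end show that the start-date half of the rule loses nothing.

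The second of the two rows covers a course taken wholly on study. If Day 1 is the 10th and the course runs from the 14th to the 21st, with both dates recorded by month only, both are treated as before first dose and the course is prior only.

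How often a reclassified record was really in use after first dose cannot be computed, because the documents give no count of incomplete dates. The following is illustration only and assumes that all possible end days are equally likely.

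- **Month-only end date, 30-day month, first dose on day d of that month.** Share of possible end days after first dose = (30 − d)/30. For d = 1 this is 29/30 = 97%; d = 15, 15/30 = 50%; d = 25, 5/30 = 17%; d = 30, 0%. The average over d = 1 to 30 is 435/900 = 48%.
- **Year-only end date, first dose on 1 March of a 365-day year (day 60).** Counting to year end, (365 − 60)/365 = 305/365 = 84%. For a drug already reported as stopped by Week 12 (target study day 85 in SAP 7.9.2), only 85 − 1 = 84 later days are possible, so the share is 84/(60 + 84) = 84/144 = 58%.

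Under SAP 7.9.6 all of these records are classed as not concomitant.

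**The case against.** The strongest reply is that the affected set is small and the consequence slight. Medications marked ongoing, or known to have started after first dose, are untouched. Protocol sections 8.2 to 8.7 collect medication use at Baseline, at the Week 2 call and at every clinic visit, and Protocol section 7 asks for start and discontinuation dates. The rule is the same in both arms, the tables are descriptive, and the records still appear in the prior-medication table. All of this stands. It limits the size of the problem but does not remove the one-way classification.

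Three stronger readings are tempting, and the documents do not support them.

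- **A reader might infer that washed-out acne products are the main casualties, because they stop near Day 1.** Protocol section 5.3.2 requires gaps such as 2 weeks for over-the-counter topicals and 4 weeks for others, for example "Treatment with systemic antibiotics or systemic anti-acne drugs within 4 weeks prior to Baseline". With a 28-day gap, stop and first dose share a calendar month only if first dose falls on day 29 or later; with 14 days, on day 15 or later. In either case a product washed out as required is truly prior, and the rule classes it correctly. The records at risk are products that were not stopped, and short on-study courses.
- **A reader might infer that the PP population is wrongly composed.** No text ties the criterion in SAP 7.8.4 to the classification in 7.9.6. SAP section 4.1.3 has violations determined before the randomization schedule is released, so a blinded review of individual records could catch these medications. Some subjects might also be excluded under "Violated the inclusion/exclusion criteria" if the medication is taken to have ended inside a washout window, but the rule assigns no actual date, so this is not assured. What remains is that 7.9.6 is the only place where the SAP defines concomitant or handles partial medication dates, and no full deviation dataset is planned as a cross-check. The PP effect is possible, not shown.
- **A reader might infer that efficacy conclusions are at risk.** ITT membership (SAP 7.8.2) depends on randomization and dispensing, not on medication use, and the stepwise secondary tests (SAP 7.6) are ITT only.

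**Conclusion.** The point holds in a limited form. By the text of SAP 7.9.6, a medication with an ambiguous end date that is not marked ongoing, and not known to have started after first dose, can only be prior. For those records the concomitant summary can be undercounted but never overcounted. That conclusion rests on the wording alone. The percentages in the working rest on the equal-likelihood assumption and say nothing about how many records are involved; that number is unknown. Any effect on PP exclusions depends on whether the PP medication review uses the 7.9.6 classification, which the documents leave open. The ITT analyses are unaffected. This is a cheap improvement, not a threat to the trial's conclusions.

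**What to change.** Keep the present rule for incomplete start dates only. For end dates, substitute: *A medication is classed as concomitant unless its available start and end date parts show that it ended on or before the date of first dose.* The words on or before matter: they leave a complete end date equal to Day 1 where SAP 7.9.6 now puts it, outside the concomitant class. Add to SAP 7.8.4 that the blinded PP medication review uses this rule; without that, the PP question stays open.

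The cost is one revised sentence in 7.9.6, one added sentence in 7.8.4 and one changed derivation. The downside is that a few truly prior medications will also appear in the concomitant table. Section 7.9.6 already allows a medication to appear in both summaries, and any such record that reaches the PP review can be judged there case by case.

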7.9.7 Efficacy Analyses

All efficacy analyses will be presented by treatment group for both ITT and PP populations.

7.9.7.1 Primary Efficacy Analyses

Absolute change from Baseline to Week 12 in inflammatory and non-inflammatory lesion counts will be analyzed using either parametric or non-parametric methods consistent with the statistical assumptions required to support the analyses. Specifically, the tests of superiority will be based on an ANCOVA with factors of treatment group and analysis center and the respective baseline lesion count as a covariate or on ranked data submitted to an ANCOVA with factors of treatment group and analysis center and the respective baseline lesion count as a covariate. If the treatment group by analysis center interaction effect is significant at an alpha less than 0.10, then the effect will be included in the model; otherwise it will be omitted.

A skewness test, based on the methods presented by J.H. Zar (1984) [1], will be applied to the residuals resulting from an ANCOVA. A two-sided p-value for the skewness test significant at 0.01 will imply the use of the non-parametric method. If a parametric analysis is indicated, the results of the parametric analysis will be considered the primary analysis. Should a non-parametric analysis be indicated, the absolute or percent changes in inflammatory and non-inflammatory lesions will be rank-transformed prior to submitting them to the ANCOVA. Results of the rank-transformed analyses then will be considered the primary analysis; however, results of the non-ranked transformed analyses will also be presented. That is, the primary analyses for inflammatory and non-inflammatory lesion counts will be determined by the treatment group by analysis center interaction p-value and the skewness p-value as described in the table below:

Determination of Model for Primary Analyses

Interaction P-Value	Skewness P-Value	Analysis Model
< 0.10	< 0.01	Ranked ANCOVA with factors of treatment, analysis center and treatment by analysis center interaction and the respective baseline lesion count as a covariate
≥ 0.10	< 0.01	Ranked ANCOVA with factors of treatment and analysis center and the respective baseline lesion count as a covariate
< 0.10	≥ 0.01	ANCOVA with factors of treatment, analysis center and treatment by analysis center interaction and the respective baseline lesion count as a covariate
≥ 0.10	≥ 0.01	ANCOVA with factors of treatment and analysis center and the respective baseline lesion count as a covariate

Note that interaction and skewness p-values will be computed for each imputation of multiply-imputed data. Model determination will depend on averaged p-values, computed by finding the mean p-values across all imputations.

The proportion of subjects who are dichotomized to success at Week 12 will be analyzed using a logistic regression with factors of treatment group and analysis center.

The sensitivity analysis for absolute change in lesion count will include a skewness test, based on the methods presented by J.H. Zar (1984) [1]. A ranked repeated measures analysis of covariance with factors of treatment group, visit, analysis center and treatment by visit interaction, and the respective baseline lesion count as covariate will also be included. Values will be ranked across all visits (i.e. visit will be ignored when ranking) and the baseline covariate will not be ranked.

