11.3 Primary Efficacy

Absolute change from baseline to Week 12 in inflammatory and non-inflammatory lesion counts will be analyzed using either parametric or non-parametric methods consistent with the statistical assumptions required to support the analyses. Specifically, the tests of superiority will be based on an ANCOVA with factors of treatment and analysis center and the respective Baseline lesion count as a covariate or on ranked data submitted to an ANCOVA with factors of treatment and analysis center and the respective Baseline lesion count as a covariate. If the treatment-by-

analysis center interaction effect is significant at an alpha less than 0.10, then the effect will be included in the model; otherwise it will be removed.

A skewness test, based on the methods presented by J.H. Zar (1984) [14], will be applied to the residuals resulting from an ANCOVA. A two-sided p-value for the skewness test significant at 0.01 will imply the use of the non-parametric method. If a parametric analysis is indicated, the results of the parametric analysis will be considered the primary analysis. Should a non-parametric analysis be indicated, the absolute or percent changes in inflammatory and non-inflammatory lesions will be rank transformed prior to submitting them to the ANCOVA. Results of the rank-transformed analyses then will be considered the primary analysis; however, results of the non-ranked transformed analyses will also be presented.

The proportion of subjects who are dichotomized to success at Week 12 will be analyzed using the logistic regression test stratified by analysis center.

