The consistency of treatment response will be investigated across the analysis centers subsequent to combining the data as described above. Statistical tests will be conducted to identify if there are extreme analysis centers that could affect the interpretation of common statistical and clinical conclusions. An analysis center by treatment interaction will be included in the primary and secondary variable analyses to test for parallel treatment effect at an alpha level of 0.10. Change from baseline in inflammatory lesions and non-inflammatory lesions will be analyzed with an ANCOVA (unranked or ranked) with factors of treatment group, analysis center and treatment group by analysis center interaction and the respective baseline lesion count variable as a covariate. For the purpose of testing consistency of treatment response, the dichotomized IGA will be analyzed with a logistic regression with factors of treatment group, analysis center, and the interaction term of treatment group by analysis center. Further examination will follow for any variables that have a significant ANCOVA or logistic regression interaction term.

In the event that the ANCOVA or logistic regression interaction (referred to henceforth as the "appropriate test") p-value is ≤ 0.10 , a sensitivity analysis that excludes analysis centers with the extreme efficacy result will be performed to determine the robustness of the treatment effect. On the other hand, if all three analyses result in interaction terms with p-values > 0.10 , then the

conclusions from the pooled data will be considered to be free of the impact of extreme analysis centers.

The first step in conducting a sensitivity analysis is to identify the extreme analysis center or centers that contribute to the statistical significance of the interaction term of the appropriate test. The process involves submitting subsets of analysis centers to the appropriate test and observing the interaction p-value for the subset. Subsets producing interaction p-values >0.10 are considered homogeneous.

The search for an extreme analysis center begins by analyzing all subsets that can be created by excluding one analysis center. If one or more of the subsets result in an interaction p-value >0.10 , then the analysis center excluded from the subset with the largest interaction p-value is deemed to be the extreme analysis center.

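### A preliminary interaction test chooses the primary lesion-count model, and the treatment contrast in the interaction model is not stated

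*SAP*

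**What the plan says.** Protocol 11.3 and SAP 7.9.7.1 analyze absolute change in each lesion count by ANCOVA with treatment, analysis center and the baseline count. Both attach a condition on the interaction. In the protocol, if it is significant below 0.10, "then the effect will be included in the model; otherwise it will be removed". The SAP keeps the rule with one word changed; below the same threshold, "then the effect will be included in the model; otherwise it will be omitted".

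This governs the primary analysis itself. The SAP states that "the primary analyses for inflammatory and non-inflammatory lesion counts will be determined by the treatment group by analysis center interaction p-value and the skewness p-value", and a four-row table sets out the combinations. On multiply imputed data, "Model determination will depend on averaged p-values, computed by finding the mean p-values across all imputations".

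Related text:

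- SAP 7.3.1.1 repeats the conditional interaction term for the analysis of the imputed data sets.
- SAP 7.9.7.2 applies the same ANCOVA method to the percent-change secondary endpoints.
- SAP 7.5 separately fits the interaction "to test for parallel treatment effect at an alpha level of 0.10", followed by a search for extreme centers.
- The IGA co-primary has no such step. It "will be analyzed using a logistic regression with factors of treatment group and analysis center".

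Neither document says how treatment is estimated or tested once the interaction is in the model. No contrast, center weights or type of sums of squares is given. SAP 7.1 names SAS, and the SAP abbreviation list contains LSMean.

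**The concern.** Without the interaction, ANCOVA gives one treatment effect in which each center counts according to its information. With the interaction, the overall treatment effect must be built from center-specific effects, and the result depends on the weights. The customary SAS Type III test and the default LSMEANS difference weight centers equally, so a center at the SAP minimum (10 active, 5 vehicle) counts as much as the largest. Under reference coding, the raw treatment coefficient would be the effect in a single reference center. The per-imputation result passed to PROC MIANALYZE is therefore not uniquely defined.

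At stake are the precision of two of the three co-primary tests and, if center effects differ, the quantity being estimated. The two lesion endpoints could also be analyzed with different models. The trigger is uncertain too, because a mean of p-values over imputations is not a test at the stated 0.10 level.

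**Working it through.** **Inputs from the documents.** Non-inflammatory difference 14.73 − 9.70 = 5.03, SD 16.72. Inflammatory difference 15.21 − 9.7 = 5.51, SD 11.00. Two-sided alpha 0.05. Planned allocation 467/233 (SAP 4.2). About 50 sites (protocol synopsis). Pooling to at least 10 active and 5 vehicle subjects (SAP 7.5).

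**Assumptions.** Site-size CVs from 0 to 1.5, because the documents give no spread. Randomization 2:1 in blocks of three within site. The within-country pooling restriction is ignored. Equal-weight contrast in the interaction model. No true interaction.

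**Step 1. The plan's own figures.** Power = Φ(difference/SE − 1.96), with SE = SD·√(1/n₁ + 1/n₂).

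- Non-inflammatory, 450/225: SE = 16.72·√(1/450 + 1/225) = 1.365; 5.03/1.365 = 3.684; Φ(1.724) = 95.8%. The plan states 95%.
- Inflammatory, 300/150: SE = 11·√(1/300 + 1/150) = 1.100; 5.51/1.100 = 5.01; Φ(3.05) = 99.9%. The plan states at least 95%.
- Non-inflammatory, 467/233: SE = 1.341; 5.03/1.341 = 3.751; Φ(1.791) = 96.3%. This is the reference value below.

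**Step 2. The two estimators.** For center k let w_k = n₁ₖn₂ₖ/(n₁ₖ + n₂ₖ), with true effect δ_k and K centers.

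- Main effects: target Σw_kδ_k/Σw_k, variance σ²/Σw_k.
- Interaction, equal weights: target Σδ_k/K, variance σ²Σ(1/w_k)/K².
- Variance ratio: Σw_k·Σ(1/w_k)/K², which is at least 1 and equals 1 only when all w_k are equal.

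If all δ_k are equal the targets coincide and only precision differs. If they are not equal, the targets generally differ.

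**Step 3. Precision if the interaction model is used** (mean of 400 simulated enrolments per CV):

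| Site-size CV (assumed) | Mean K | Variance ratio | SE ratio | Non-inflammatory power, equal weights |
|---|---|---|---|---|
| 0 | 25.0 | 1.001 | 1.001 | 96.3% |
| 0.3 | 35.3 | 1.025 | 1.013 | 95.9% |
| 0.5 | 34.6 | 1.052 | 1.026 | 95.5% |
| 0.75 | 30.3 | 1.104 | 1.051 | 94.6% |
| 1.0 | 26.0 | 1.146 | 1.070 | 93.8% |
| 1.5 | 21.2 | 1.287 | 1.134 | 91.0% |

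Main-effects power is 96.3% in every row. Inflammatory power is at least 99.9% throughout with either model.

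**Step 4. How often chance selects the interaction.** With complete data, 20,000 simulated trials per scenario gave 9.6% to 10.5% per endpoint. For at least one of the two lesion endpoints, independence would give 1 − 0.9² = 19%.

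The SAP's mean-p rule was then simulated at a CV of 0.75 (1,500 trials, 30 imputations, within-arm imputation from baseline with an assumed correlation of 0.5). Selection was about 8%, 7% and 3% per endpoint with 5%, 10% and 20% missing (assumed). Under independence, at least one endpoint switches in 1 − 0.92² = 15%, 1 − 0.93² = 14% and 1 − 0.97² = 6%. Averaging makes the switch rarer and ties its frequency to the amount of missing data.

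**Step 5. Net effect of the two-step rule** (complete data):

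| CV | Type I error, two-step | Power, two-step | Power, main effects |
|---|---|---|---|
| 0.3 | 4.9% | 96.6% | 96.6% |
| 0.75 | 5.0% | 96.2% | 96.3% |
| 1.0 | 5.1% | 96.1% | 96.3% |

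Among the roughly 2,000 triggered null trials per scenario, the equal-weight test rejected in 4.3%, 6.1% and 5.5%. At a CV of 1.5 the average power loss is roughly 0.10 × (96.3 − 91.0) = 0.5 point with complete data, or 0.08 × 5.3 = 0.4 point at the selection rate for 5% missing.

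**The case against.** The strongest defense is that the rule is fully prespecified. The thresholds and a four-row table are fixed in advance, and the error rate and average power are barely touched. That stands, and it limits the weight of the point.

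Four stronger readings are tempting, and the documents do not support them.

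- *The SAP prescribes an unweighted mean over centers.* It does not. Equal weighting is inferred from usual SAS behavior; the documented gap is that no contrast is given.
- *Chance changes the estimand in 10% of trials per endpoint, or 19% for at least one.* Those are complete-data rates, and the 19% also assumes independence. With no true interaction the unranked target does not change. It changes only when center effects really differ, and then selection is not purely chance.
- *The preliminary test inflates type I error.* Overall it does not: 4.9% to 5.1% in the simulations.
- *The interaction term can add nothing.* That was not tested. Every simulation assumed no true interaction; with real heterogeneity the term could remove some residual variation.

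The defense does not answer the missing contrast. Prespecifying the model terms does not define the treatment test when the model contains an interaction. SAP 7.5 already provides a place to examine heterogeneity.

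**Conclusion.** The point holds as a minor one. A preliminary test decides the form of the primary lesion-count model, and the treatment contrast for one of the two forms is undefined.

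Under an equal-weight contrast and no true interaction, a triggered switch costs precision only. For non-inflammatory lesions, power goes from 96.3% to between 95.9% and 91.0% for assumed site-size CVs of 0.3 to 1.5. There is essentially no loss with equal-sized sites, and the inflammatory endpoint is essentially unaffected. Chance selection is at most about 10% per endpoint. Averaged over all trials, the power loss is below 0.2 point at the simulated CVs up to 1.0 and about half a point at 1.5, with no material type I error inflation.

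If center effects truly differ, the data also select which average effect is estimated. The size of that effect was not evaluated.

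The results rest on about 50 sites, the SAP pooling rule without its country restriction, and assumed enrolment spread and missingness. The case for change is a fixed, interpretable primary analysis, not a threat to the trial's error rates.

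**What to change.** Make ANCOVA with treatment, analysis center and baseline lesion count the primary model in all cases, ranked or unranked by the existing skewness rule. Specifically:

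- SAP 7.9.7.1: delete the conditional interaction sentence, the two table rows with an interaction p-value below 0.10, and the averaged interaction p-value.
- SAP 7.3.1.1: remove the matching conditional term.
- SAP 7.9.7.2: confirm that the percent-change secondaries use the same fixed model.
- SAP 7.5: reword so that the interaction is fitted only as a separate consistency check, reported with center-specific effects.
- SAP section 5: record the departure from protocol 11.3 before unblinding.

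If the conditional model is kept, the minimum repair is to state the treatment contrast and center weights used in it.

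The cost is wording only, with no change to data collection or sample size. What is given up is the option of an interaction-adjusted primary test if centers truly differ; the check under SAP 7.5 still shows such heterogeneity.
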